- Randomized: defined as any family member who's loved one has the statuses of RELEASED, APPROVED, and CONSENTED, the family member completes T1 survey, and continues to meet all eligibility criteria. Family members who reach this status will be required to interact with the app three additional times (i.e., completion of T2, T3, and T4). Additionally, if the family is randomized to Arm 1, they will be required to participate in at least one family meeting conducted by the ICU attending. Patients and family members who are assigned this status must be maintained on the enrollment log.
 - Responder: defined as any family member who is randomized to the intervention arm and upon completing survey 2 (T2) received a NEST score of <25 and their survey 2 (T2) score is less than their survey 1 (T1) score. Individuals who are assigned this study status will not receive a Palliative Care consult by the Palliative Care clinician. Only the ICU attending will be able to view the survey results.

 - Non-responder: defined as any family member who is randomized to the intervention arm and upon completing survey 2 (T2) received a NEST score of >25 or their survey 2 (T2) score is greater than their survey 1 (T1) score. Individuals who are assigned this study status are to receive a Palliative Care consult by the Palliative Care clinician. The family member's survey results will be viewed by both the ICU attending and the Palliative Care clinician.
- Screen Failed: defined as any family member who was consented to the study, completes survey 1 (T1), but DOES NOT receive a NEST score of ≥ 10 on completion of survey 1 (T1). Patients and their family members who are assigned this status must be maintained on the enrollment log.
- Withdraw by PI or Self: defined as any family member who voluntarily consents to participate in the study, but is then withdrawn from the study. The PI may withdraw a participate at any time without their consent if the PI deems it is in their best interest to no longer participate OR the individual demonstrates lack of compliance with study protocol and study procedures. Family members who reach this status have no additional follow-ups or study requirements; no further clinical data will be abstracted from the patient's EMR. Patients and family members who are assigned this status must be maintained on the enrollment log.
- Lost to Follow-Up (LTF): defined as any family member who voluntarily consents to participate

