We will test the primary study hypothesis that the NEST score is lower (i.e., fewer unmet needs) for intervention family caregivers compared to usual care at T3 (~1-week post-randomization). All participants will be analyzed as part of the group they were assigned, regardless of adherence or crossover status (i.e., intention to treat). We will use a general linear model to estimate mean NEST changes and corresponding confidence intervals over time using SAS PROC MIXED (SAS Institute, Cary NC). Different correlation structures will be examined (e.g., unstructured, autoregressive) and model fit indices will be used to guide the choice of the final model's structure.

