Analyses similar to those conducted for the NEST (primary outcome analyses) above will be performed for the secondary family caregiver hypotheses involving PHQ-9, GAD-7, and PTSS scores at T3 and T4. While family caregivers will be interviewed at T4 regardless of patient survival, patient death could complicate the analyses in two key ways: (1) Presence of missing data due to family loss to follow up (i.e., non-random missing data) and (2) differences in family caregiver distress by patient survival status (i.e., heterogeneous effect). 35 To address the impact of patient death on outcomes, after first exploring reasons for and predictors of dropout, we will conduct a 2-step supplemental analysis. In Step 1, missing T4 data due to loss to follow up among family caregivers of survivors will be multiply imputed via SAS PROC MI. In Step 2, we will account for T4 outcomes that are missing due to death via composite endpoint and principal stratification methods to estimate the causal effects of the intervention in the presence of these unidentified outcomes and complicated missing data patterns. 36,37 For the key patient outcome, receipt of goal concordant care, we will use logistic regression models adjusting for the stratification variables, to examine if rates at T3 differ by treatment group. The key healthcare systems outcome, post-randomization hospital length of stay (LOS), provides a unique challenge due to the high expected mortality rate (40-50%). In addition to descriptive analyses, steps to examine treatment group LOS differences will include: (1) a proportional hazards model with death treated as a censoring event; (2) a chi-square test of mortality rate differences; and (3) a Brunner-Manzel rank test for the composite death-LOS outcome. This last step implements a recently developed methodology of a composite outcome that incorporates a numerical value for death (i.e., coded as the worst possible outcome or the longest possible stay) in the observed LOS distribution. 38,39

Aim 3

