One of these study staff will then contact the participant. Contact is to occur as soon as possible (and definitely within 24 hours of learning of the event). Using the full C-SSRS, the trained staff will then help to assess the participant to determine if they endorse active suicidal ideation. The trained staff will also determine if the participant is currently being treated by a mental health professional.

If the participant is considered to be *actively suicidal* then at least one of the following plans will be followed depending on the location of the participant for each of the following situations:

Situation 1

- If the participant is with one of the study personnel, the study personnel will notify the PIs immediately.
- The study personnel will either physically walk the subject to the emergency department, or call a Psychiatric Emergency services number relevant to the site as described above.

Situation 2

- o If the participant is on the telephone:
 - The study personnel will notify the PIs immediately
 - The study personnel will stay on the telephone with the subject participant.
 - The study personnel will immediately contact 911 to initiate an on-site rescue if such action is clinically indicated.
- The study personnel will stay on the telephone with the subject until EMS services have contacted the participant.

Situation 3:

- If there are any active suicidal concerns in any of the surveys (e.g., PHQ-9 above), an email, or in a text message:
 - The study data system will notify the PIs and Study Manager in real time of any PHQ-9 suicidality item positively endorsed.
 - The study personnel will then contact the honest broker to de-identify the participant information.
 - Next, the study personnel (or a PI; whoever is able first) will contact the participant by telephone.
 - The study personnel or PI will stay on the telephone with the subject participant
 - The study personnel or PI will use a different telephone line to immediately contact 911 to initiate an on-site rescue if action is clinically indicated.
 - The study personnel or PI will stay on the telephone with the subject until EMS services have contacted the participant.

If the participant if determined to be actively suicidal and require immediate medical therapy, they will be withdrawn from the study.

If the family member is deemed not to be actively suicidal, they will be given a list of local mental health resources within the app platform's screen as follows:

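### Withdrawal by the PI, including for non-compliance, ends EMR data collection as well as surveys, at odds with the intention-to-treat, event follow-up and mortality-monitoring commitments

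*Combined protocol and SAP*

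**What the plan says.** - **Section 5, status entry for withdrawal by PI or self.** The PI may remove a caregiver at any time without consent, either in the caregiver's best interest or because "the individual demonstrates lack of compliance with study protocol and study procedures". The consequence is stated in one sentence: "Family members who reach this status have no additional follow-ups or study requirements; no further clinical data will be abstracted from the patient's EMR".
- **Section 10, Suicidality Response Plan.** A caregiver found to be "actively suicidal and require immediate medical therapy, they will be withdrawn from the study". The plan does not name the resulting status, but section 5 defines only one withdrawn status.
- **Section 5, lost to follow-up.** This is a separate status, reached after non-compliance and at least three documented contact attempts. The caregiver may resume within a week. It ends follow-up but has no sentence stopping EMR abstraction.
- **Section 8, Aim 2 analysis.** "All participants will be analyzed as part of the group they were assigned, regardless of adherence or crossover status". For missing data, "missing T4 data due to loss to follow up among family caregivers of survivors will be multiply imputed via SAS PROC MI", and outcomes missing because of death are handled separately. Withdrawn caregivers are not mentioned.
- **Section 11, event follow-up.** Events are followed until they resolve or stabilise.
- **Section 12, DSMB.** Three-month all-cause mortality is the main adverse event for patients, with looks at 15, 25 and 50 deaths. Appendix 3 obtains survival status from EMR review, a telephone interview, or both.

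**The concern.** A commitment to analyse people whatever their adherence needs outcome data on those who do not adhere. Here non-adherence is itself a ground for ending data collection, and it ends the patient's record data because of the caregiver's conduct. Hospital length of stay, discharge disposition, hospice use and death can all be read from the EMR without any action by the caregiver, so losing them is avoidable.

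The loss may also be selective. Withdrawal is discretionary, non-compliance is not defined, and section 5 has the study team told of the arm at randomisation. Only Arm 1 caregivers have a required family meeting. If withdrawals differ in number or in prognosis between arms, the systems outcomes and the mortality comparison rest on a selected subset, and the missing-data plan in section 8 does not address it.

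**Working it through.** **1. The passages side by side**

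| Commitment | Effect of withdrawn status |
|---|---|
| Analyse as assigned whatever the adherence (section 8) | Data stop because of non-adherence |
| Follow events until settled (section 11) | No further follow-up, including after a suicidality event |
| Three-month mortality as main patient adverse event (section 12) | Both sources in Appendix 3, EMR and telephone, are closed |
| Imputation of T4 loss to follow-up among caregivers of survivors (section 8) | Withdrawn dyads not named |

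No section separates stopping study activity from stopping data collection.

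**2. The plan's own figure**

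Inputs from section 8: difference 8.80, SD 21.1, correlation 0.64, type I error 5% (taken as two-sided), 65 per arm.

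- SD of change = 21.1 × √(2 × (1 − 0.64)) = 17.90.
- This gives 65 per arm and 80.0% power, so the stated figure reproduces.
- Standard error of the difference = 17.90 × √(2/65) = 3.14.

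**3. Possible shift in NEST**

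If a fraction p of an arm is removed and their mean lies D points above the rest, that arm's mean moves by p × D. With the same D in both arms, the treatment difference moves by (net imbalance in p) × D. The documents give neither quantity. Assume a net imbalance of 1–5% and D of 5–15 points:

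- Low end: 0.01 × 5 = 0.05 points, and 0.05 / 8.80 = 0.6%.
- High end: 0.05 × 15 = 0.75 points, and 0.75 / 8.80 = 8.5%.
- High end against the standard error: 0.75 / 3.14 = 0.24.

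The direction depends on which arm loses more people and whether they have higher or lower need. If high-need caregivers are removed from Arm 1, the shift favours the intervention.

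**4. Power**

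- 130 / 0.9 rounds up to 145, and 150 are to be randomised.
- At 10% dropout, 150 × 0.9 = 135 complete, giving 81.5% power.
- With 5 further losses power is 80.0%; with 8 it is 79.1%.

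**5. Deaths not seen**

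Section 8 expects 40–50% mortality and does not state the period. A net 1–5% of an arm of 75 is 0.75 to 3.75 patients. The unobserved deaths would number at most 0.75 × 0.40 = 0.3 to 3.75 × 0.50 = 1.9, fewer if some patients died before withdrawal. The looks are at 15, 25 and 50 deaths.

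**The case against.** Several stronger readings are tempting, and the documents do not support them.

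- **That intention to treat becomes impossible, or that withdrawn caregivers are excluded.** Section 8 fixes the group in which people are analysed, and section 5 stops only later data. NEST scores already given can enter the mixed model in the assigned arm. The problem is avoidable missing data, not exclusion.
- **That the suicidality route strips the worst PHQ-9 scores from the PHQ-9 outcome.** Withdrawal there needs both active suicidality and a need for immediate medical therapy, and section 10 reports no acute psychiatric referrals in earlier similar studies. Appendix 5 collects PHQ-9 at T1, T3 and T4. A trigger at T3 comes after that score is entered, so it mainly costs T4 and later EMR data. The T3 score is lost only after a T1 trigger or a concerning contact before T3.
- **That non-compliance withdrawal will be common, because late surveys are expected.** Section 11 does not count missed or late surveys as deviations, the PI's power is discretionary, and the lost-to-follow-up status is the more natural route for non-responders.
- **That Arm 1 will lose more people.** Survey duties are the same in both arms. The ICU attending initiates the meeting, and section 11 treats failure to hold one as a clinician's deviation. Imbalance is possible but not shown.
- **That power is at risk.** Step 4 shows otherwise.

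It is also fair that a caregiver who will not complete surveys has no T3 NEST under any wording, and that the mixed model recovers some information from earlier scores. The NEST shift is therefore only partly attributable to this rule.

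What stands is that the withdrawal entry closes the EMR for a reason unrelated to the patient, on an undefined ground applied with the arm known, and nothing elsewhere restores those outcomes or says how withdrawn dyads are analysed.

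**Conclusion.** The concern holds as an inconsistency between the withdrawal entry in section 5 and the commitments in sections 8, 11 and 12. It bears mainly on length of stay, disposition, hospice use and mortality. The non-compliance ground carries it; the suicidality route is expected to contribute close to nothing.

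On the assumed ranges the NEST difference moves by 0.05–0.75 points, under 9% of 8.80 and at most about a quarter of a standard error. The loss of power is negligible. These sizes rest on an assumed net imbalance of 1–5% and a gap of 5–15 points, since no withdrawal rate is given. Severity: minor.

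**What to change.** Reconcile the withdrawal entry in section 5 with the Suicidality Response Plan in section 10, the analysis plan in section 8, event follow-up in section 11 and mortality monitoring in section 12:

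1. Separate the end of study activities from the end of data collection.
2. Continue EMR-based outcomes and vital status for every randomised dyad unless consent for data use is withdrawn.
3. Remove non-compliance as a ground for ending data collection.
4. State in section 8 that withdrawn dyads are analysed as assigned, and add a sensitivity analysis for their missing outcomes.

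The suicidality response, and whether surveys are offered after it, stay with the sponsor and the IRB; no change to either is proposed here.

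The cost is a wording change, a little more abstraction, and a check that the consent text permits continued EMR use after PI withdrawal. That text is not in the copy reviewed, so this has not been confirmed.

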Duke: Call Emergency Psychiatry at [contact] or [contact], available 24 hours a day, 7 days a week.

Protocol Version: 5.1 Dated: 13 June 2022 Page 18 of 42

• The National Suicide Prevention Lifeline - [name] is a free, 24-hour hotline available to anyone in suicidal crisis or emotional distress.

As described above, all concerns about participant safety will be discussed immediately with the PIs - including concerning severe distress that does not involve suicidality.

For these situations, once an "alert situation" is known, the PIs will refer the participant if needed (based on a PI-led phone call) to local psychological resources. The study team will also make urgent and emergency referrals as needed based on information learned.

To date, in previously completed similar studies, analysis has found that <5% of participants will require a call from the study team during some point in the study period. Of those, none have required referral to acute psychiatric care after a detailed interview from the study team. After a disposition/solution has been made, both the resolution (and follow up) will be documented in the 'contact log' section of the data system for reporting to the DSMB.

Patient Death While in Study

Finally, it is recognized that this project targets patients who are critically ill and elderly, therefore, there is a risk of death. The study team will review the EMR to look for records of death, halting all study procedures, if applicable, and noting the date of death. Additionally, on phoning any family member, the study team will initiate a conversation to tactfully ascertain the patient's vital status. If the patient has died, we will provide brief support. If a family member states that they wish to drop out, the study team will respect that as well. A follow-up question may be asked to ascertain the reason for withdraw; however, this is for documentation purposes only.

Vulnerable Populations

The study team not enroll patients from vulnerable populations (e.g., imprisoned persons, minors). However, elderly patients will be targeted for enrollment into this project, and therefore, there is a potential risk of death due to their age and critical illness in < 3 months.

Potential Benefits

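### The instruction to stop study procedures when a patient dies conflicts with the plan to survey every caregiver at T4, and the T4 analysis text does not settle which applies

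*Combined protocol and SAP*

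**What the plan says.** Three pieces of current text in the combined protocol and SAP bear on this.

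- **Conduct rule.** Section 10, Patient Death While in Study, gives the instruction to staff: "The study team will review the EMR to look for records of death, halting all study procedures, if applicable, and noting the date of death". The qualifier is not defined and no procedure is listed as exempt. The same paragraph adds: "If a family member states that they wish to drop out, the study team will respect that as well".
- **Follow-up rule.** Section 8, Aim 2 analysis: "While family caregivers will be interviewed at T4 regardless of patient survival, patient death could complicate the analyses".
- **Missing-data plan.** The same paragraph of section 8 sets out a two-step supplemental analysis. Step 1 imputes "missing T4 data due to loss to follow up among family caregivers of survivors". Step 2 deals with "T4 outcomes that are missing due to death", using composite-endpoint and principal-stratification methods.

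Section 8 also gives an expected mortality of 40–50%, in the length-of-stay discussion and without a time horizon. Appendix 5 collects PHQ-9, GAD-7 and PTSS at T1, T3 and T4, and NEST at T1, T2 and T3 only.

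**The concern.** The caregiver is the main research subject, and the surveys are that person's main study task. A coordinator who takes section 10 at its word would stop sending surveys once the patient has died. One who works from section 8 would send T4. Step 2 of the missing-data plan adds to the doubt. It treats caregiver T4 outcomes as lost through the patient's death, although a caregiver's own PHQ-9 can still be obtained.

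If the halt is applied to surveys, T4 distress scores go missing according to a post-randomisation event. Section 8 itself expects distress to differ by patient survival, so the lost scores would not resemble those kept. Section 12 says higher mortality in the intervention arm is possible, while noting that past end-of-life interventions have not increased it. If survival does differ by arm, comparing survivors' caregivers is no longer a randomised comparison. If it does not, the comparison still answers a narrower question than the intention-to-treat one in section 8.

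The loss could also pass unremarked, because section 11 says missed surveys are not protocol deviations.

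**Working it through.** **1. The plan's own figures.** Section 8, Sample Size and Power, gives 65 per arm at 8 days, 80% power and 5% type I error (two-sided assumed). For NEST it gives 8.80 units, SD 21.1, ρ = 0.64. For PHQ-9 it gives 2.33 units, SD 5.3, ρ = 0.6.

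SD of change = SD × √(2(1 − ρ)); power = Φ(δ / (SD of change × √(2/n)) − 1.96), with n per arm.

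- NEST: 21.1 × √0.72 = 17.90; at n = 65, power 80.0%.
- PHQ-9: 5.3 × √0.80 = 4.74; at n = 65, power 80.0%.

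Both reproduce. With 150 randomised, 10% dropout and no halt at death, 150 × 0.90 = 135 are evaluable and power is 81.5%.

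**2. T4 if surveys stop at death.** Assumptions: the 40–50% applies by day 90; a further 10% of the remaining caregivers drop out; the 8-day SD and correlation hold at T4. The plan gives no T4 dropout rate, SD or correlation.

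| Mortality by day 90 | Caregivers losing T4 | Remaining | After 10% dropout | Power, 2.33 PHQ-9 units | Difference detectable at 80% power |
|---|---|---|---|---|---|
| 40% | 0.40 × 150 = 60 | 90 | 81 | 60% | 2.95 |
| 50% | 0.50 × 150 = 75 | 75 | 67.5 | 52% | 3.23 |

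**3. Primary NEST at T3.** No text says whether T2 and T3 surveys go out after a death, and the share of patients dead by day 8 is not given. With an assumed share d, evaluable N = 150 × (1 − d) × 0.90.

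| Assumed d | N | Power, 8.80 NEST units |
|---|---|---|
| 5% | 128 | 79.5% |
| 10% | 121.5 | 77.3% |
| 20% | 108 | 72.4% |

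Only deaths after T1 matter, since section 4 excludes patients who die before T1 is completed. Appendix 4 makes T3 contingent on T2, so a halt before T2 would remove T3 as well.

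These figures count a missing survey as a complete loss. The planned mixed model would use a caregiver's earlier scores, so the power loss may be somewhat smaller. It would do so by assuming that, given earlier scores, bereaved caregivers follow the course of the others.

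**The case against.** The best case for the plan is that, read as a whole, it points towards continued follow-up. The halt is qualified. Respecting a wish to drop out presupposes that other bereaved caregivers carry on. Section 4 makes patient death an exclusion only before T1. The status list in section 5 expects every randomised family member to complete T2, T3 and T4, and has no status for a patient's death. Survey alerts run automatically from T1 (Appendix 3). The workflow figure in Appendix 1 and most of Appendix 4 could not be read here and may show a pathway after death. All of this stands. A reader might infer that surveys will stop at death; the documents do not support that. What remains is that none of these places says which procedures the halt covers.

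A reader might also infer that the primary analysis is underpowered for this reason. That is not supported either. The follow-up commitment in section 8 covers T4 only, where NEST is not collected. The 40–50% cannot be carried to day 8, and at 5% deaths power is almost nominal. Nor is a NEST completed after death plainly usable: section 3 says the scale covers the patient's needs as well as the caregiver's, and no score after death is defined.

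Finally, the composite and principal-stratification analyses could be said to cover the gap. They are supplemental and rest on strong assumptions, which is a poor exchange for scores that could be collected.

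**Conclusion.** The concern holds as an unresolved conflict between sections 10 and 8, made worse by missing-data text in section 8 that does not fit its own follow-up rule. The documented conflict concerns T4 and so the secondary distress outcomes. If the halt is applied to surveys, up to 60–75 of 150 caregivers lose T4, and power for 2.33 PHQ-9 units is about 52–60%. This rests on the day-90 reading of the mortality figure and the borrowed 8-day inputs. Bias matters more than power, because the loss follows an event that could differ by arm. For the primary T3 NEST the documents are silent rather than contradictory, and the range of about 79.5% to 72% depends wholly on the assumed 5–20% of deaths by day 8.

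**What to change.** Reconcile the two sections in one amendment:

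1. In section 10, limit the halt to procedures that need a living patient. State that the caregiver stays in the study and is sent each remaining survey unless they decline. Section 8 already says this for T4; T2 and T3 need to be named. Keep recording the date of death, so that status at each survey is known.
2. In section 8, state in advance how a NEST completed after the patient's death enters the primary analysis.
3. In section 8, revise the two-step missing-data text so that the category of outcomes lost to death, and the restriction of imputation to survivors' caregivers, match outcomes that are still collected after a death.

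The cost is a short amendment and a coordinator instruction; the surveys are already scheduled, so no visits are added. The NEST rule needs some thought beyond wording. The small downside is that survey reminders will reach bereaved families, who may decline.
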